3 STUDY DESIGN

3.1 OVERALL DESIGN

Our plan is to study fostamatinib for the treatment of immune-mediated posttransplant cytopenias (anemia, thrombocytopenia or both)

- This will be a multicenter, open label, phase II study, with no control arm with the primary objective to test the efficacy of fostamatinib in the treatment of posttransplant cytopenias.
- All study participants will receive fostamatinib 100 mg BID for 4 weeks. On the 4-week evaluation, a) if the cytopenia improves (hemoglobin ≥ 10 g/dL, platelets $\geq 50 \times 10^9/L$), patients will continue the same dose for a total of 12 weeks b) if refractory cytopenias persist (hemoglobin < 10 g/dL, platelets $< 50 \times 10^9/L$), subjects will increase dose to 150mg BID. Subjects with persistent (≥ 2 readings, 2 weeks apart) loss of hematologic response after week 5 can increase the study drug dose to 150mg BID until they are at the end of the study on week 12.
- This trial will be done primarily in an outpatient setting. Follow up visits will be completed as outpatient in-person visits at the participating site or via telehealth or telephone if patients are unable to travel for any reason, with labs drawn by local providers in this circumstance.
- The 4-week assessment is the first milestone where dose can be adjusted if necessary. At the end of the trial, participants with objective hematologic recovery will be given the option to enroll onto an extended access trial, including:
 - Post-transplant anemia who achieved a hemoglobin ≥ 9 g/dL (or 1 g/dL above baseline) without transfusion support, at least once in the 12-week phase II study period

Abbreviated Title: Fostamatinib for post-transplant cytopenias

Version Date: 11/28/2023

- Post-transplant thrombocytopenia who achieved a platelet count $\geq 30 \times 10^9/L$ (or $10 \times 10^9/L$ above baseline), without transfusion support, at least once in the 12-week phase II study period
 - Either of the above in subjects with Evans syndrome
- The plan is to treat and include a total of 20 patients in the analysis in this single arm trial.

3.2 SCIENTIFIC RATIONALE FOR STUDY DESIGN

Post-allogeneic hematopoietic stem cell transplant (HCT) cytopenias often result from immunologic causes, where adequate bone marrow precursor cells exists but RBCs and/or platelets are peripherally destroyed by antibody mediated processes or their production is suppressed as a consequence of graft versus host disease (GVHD) [2]. Autoimmune cytopenia is a well-recognized manifestation of chronic GVHD (cGVHD) that usually occurs in the presence of other clinical signs of cGVHD [3, 4]. Several treatment options used to treat posttransplant cytopenias have been extrapolated from therapies used to manage idiopathic thrombocytopenic purpura (ITP) and autoimmune hemolytic anemia (AIHA) guidelines.

Fostamatinib, a spleen tyrosine kinase (Syk) inhibitor with the active metabolite R406, has been shown to reduce antibody-mediated platelet destruction [8]. It was FDA approved in April 2018 for patients with chronic ITP who had an insufficient response to a previous treatment. Additionally, it is currently being studied in a phase III clinical trial for subjects with warm autoimmune hemolytic anemia (NCT03764618) and in an early phase chronic GVHD trial (NCT02611063). This phase II trial is designed to evaluate the efficacy of the novel Syk inhibitor (fostamatinib) in the treatment of posttransplant cytopenias as assessed by hematologic improvement in anemia and/or thrombocytopenia following a 12-week treatment course.

3.3 JUSTIFICATION FOR DOSE

The dose was based on prior FDA approval of fostamatinib use in chronic ITP and the ongoing phase III trial for wAIHA. The starting dose is 100 mg BID which can be increased to 150 mg BID if still refractory on the 4-week evaluation. Taper and dose modification are described in details in Section 5.1.2.3.

4 OBJECTIVES AND ENDPOINTS

OBJECTIVES	ENDPOINTS	JUSTIFICATION FOR ENDPOINTS
Primary		
Efficacy of fostamatinib for stable hematologic recovery during post-hematopoietic stem cell transplant immune mediated anemia and/or thrombocytopenia.	
 • The proportion of subjects with hematologic recovery that is stable, defined as improvement documented in 2 consecutive available readings at least 2 weeks apart, without recent blood product transfusion support in the past 7 days. 
Hematologic recovery is defined as:
 
 • Hemoglobin ≥ 10 g/dL (or at least ≥ 2 g/dL above 	The endpoints are all clinically relevant to answer the trial hypothesis and indicative of clinical recovery. The endpoints were chosen to be similar to the previous FIT trials that led to FDA approval of fostamatinib in chronic ITP.

Abbreviated Title: Fostamatinib for post-transplant cytopenias

Version Date: 11/28/2023

	
baseline^{&}) in subjects with posttransplant anemia. In subjects with symptomatic anemia*, a hemoglobin increase of at least ≥ 2 g/dL above baseline is required
 
OR
 
 • Platelets $\geq 50 \times 10^9/L$ (or at least $\geq 20 \times 10^9/L$ above baseline) in subjects with posttransplant thrombocytopenia 
OR
 
 • Both of the above criteria in subjects with posttransplant Evans syndrome 	
Secondary		

Efficacy of fostamatinib for clinically-relevant outcomes in post-hematopoietic stem cell transplant patients
	
1. Proportion of subjects who achieve objective hematologic recovery within the 12-week treatment course defined as:
 
 • Hemoglobin ≥ 9 g/dL (or at least ≥ 1 g/dL above baseline) in subjects enrolled with anemia or at least ≥ 1 g/dL above baseline in subjects with symptomatic anemia 
OR
 
 • Platelets $\geq 30 \times 10^9/L$ (or at least $\geq 10 \times 10^9/L$ above baseline) in subjects enrolled with thrombocytopenia 
OR
 
 • Either of the above criteria in subjects with Evans syndrome 
2. Average weekly requirement of transfused blood component or growth factor requirement (total units of PRBC or Platelets/week, total dose of growth factor/week)
	
The secondary endpoints are all relevant to safety of fostamatinib for post-hematopoietic stem cell transplant setting

	
by week 12, compared to the week prior to the start of the study drug.
 
 3. Change in corticosteroid dose over time, measured by median daily weight-based prednisone-equivalent corticosteroid dose in a week, from week 1 to week 12 4. Change in other immunosuppressant dose over time, measured by median daily dose of the immunosuppressant in a week, from week 1 to week 12 5. Number of patients who achieved $\geq 50\%$ steroid dose reduction by week 12 compared to week 1 6. Incidence and severity of cGVHD according to 2014 NIH Consensus Criteria, at baseline before the initiation of treatment, and at week 12 	
Tertiary/Exploratory		
The exploratory objective is to evaluate changes in serologic marker while on treatment to identify key biological pathways impacted by fostamatinib that may lead to a response to therapy	
 1. Absolute percentage change in B cell chimerism pre-treatment, vs weeks 4 and 12. 2. cPRA change in the preformed HLA antibodies before and after treatment in subjects with thrombocytopenia or Evans syndrome 3. Percent MFI change of preformed HLA antibodies before and after treatment. This applies for antibodies with an MFI $>1,000$. 4. Anti-RBC alloantibody titer change in patients with hemolytic anemia before and after treatment 5. Assessment of serial cytokines pre-treatment and weeks 4 and 12. Cytokines include CRP, IL-1, IL-2, IL-6, IFNγ, TNFα, EPO and TPO 6. Immunoglobulin level changes pre-treatment, and weeks 4 and 12. 	These exploratory endpoints are relevant to the ex vivo and in vitro analysis that will help predict response and define mechanisms of action of fostamatinib for resolving cytopenias

	
7. Absolute reticulocyte count, lactate dehydrogenase, haptoglobin changes pre-treatment, and at each biweekly study visit, in patients with anemia or Evans syndrome
 
8. Change in the weekly rate and severity of bleeding according to the total score of the IBLS, from week -1 (one week before the start of the study drug) to week 12, in subjects with thrombocytopenia or Evans syndrome[#]
	
--	--	--

&: Baseline is defined as the mean of the last two hemoglobin or platelet measured at least 24 hours apart, at least 72 hours from the last transfusion, within 14 days of the start of the study drug

*: Symptomatic anemia is defined as anemia with fatigue, weakness, shortness of breath, palpitations/fast heartbeat, lightheadedness, and/or chest pain, and these symptoms are attributed to anemia

#: the IBLS [1] is a bleeding score system that assess 11 different sites of bleeding by site-specific scales

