	
 • Hemoglobin ≥ 9 g/dL (or at least ≥ 1 g/dL above baseline) in subjects enrolled with anemia or at least ≥ 1 g/dL above baseline in subjects with symptomatic anemia 
OR
 
 • Platelets $\geq 30 \times 10^9/L$ (or at least $\geq 10 \times 10^9/L$ above baseline) in subjects enrolled with thrombocytopenia 
OR
 
 • Either of the above criteria in subjects with Evans syndrome 
 2. Average weekly requirement of transfused blood component or growth factor requirement (total units of PRBC or Platelets/week, total dose of growth factor/week) by week 12, compared to the week prior to the start of the study drug. 3. Change in corticosteroid dose over time, measured by median daily weight-based prednisone-equivalent corticosteroid dose in a week, from week 1 to week 12 4. Change in other immunosuppressant dose over time, measured by median daily dose of the immunosuppressant in a week, from week 1 to week 12 5. Number of patients who achieved $\geq 50\%$ steroid dose reduction by week 12 compared to week 1 6. Incidence and severity of cGVHD according to 2014 NIH Consensus Criteria, at baseline before the initiation of treatment, and at week 12 
Exploratory endpoints:
 
 1. Absolute percentage change in B cell chimerism pre-treatment, vs weeks 4 and 12. 2. cPRA change in the preformed HLA antibodies before and after treatment in subjects with thrombocytopenia or Evans syndrome 3. Percent MFI change of preformed HLA antibodies before and after treatment. This applies for antibodies with an MFI $>1,000$. 4. Anti-RBC alloantibody titer change in patients with hemolytic anemia before and after treatment 5. Assessment of serial cytokines pre-treatment and weeks 4 and 12. Cytokines include CRP, IL-1, IL-2, IL-6, IFNγ, TNFα, EPO and TPO 6. Immunoglobulin level changes pre-treatment, and weeks 4 and 12. 7. Absolute reticulocyte count, lactate dehydrogenase, haptoglobin changes pre-treatment, and at each biweekly study visit, in patients with anemia or Evans syndrome 8. Change in the weekly rate and severity of bleeding according to the total score of the ITP-Bleeding Scale (IBLS), from week -1 (one week before the start of the study drug) to week 12, in subjects with thrombocytopenia or Evans syndrome

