5.1 INCLUSION CRITERIA

- Ages 18-75 years inclusive
- Ability to comprehend the investigational nature of the study and provide informed consent
- Female patients of reproductive potential agree to avoid pregnancy through abstinence or the use of two forms of highly effective birth control during and for 1 month after the last study treatment and agree not to donate eggs during this time
- Male patients of reproductive potential agree to avoid pregnancy of a partner through abstinence or the use of two forms of highly effective birth control during and for 1 month after the last study treatment and agree not to donate sperm during this time.
- Diagnosis of an immune mediated cytopenia (anemia and/or thrombocytopenia)[‡] in a patient that either:
 - Failed or relapsed after at least one line of therapy including steroids, IVIG, TPO mimetics, rituximab, azathioprine, cyclophosphamide, cyclosporine, tacrolimus, danazol, vincristine, ESA or splenectomy
 - Or remains transfusion dependent (≥ 1 transfusion(s)/2 weeks)
 - Or is steroid dependent*
- Subjects are ≥ 60 days post-allogeneic transplant with:
 - Thrombocytopenia, defined as average platelets count $< 30 \times 10^9/L$ for 3 consecutive available readings at least 2 weeks apart, after other cell lines have engrafted, with no counts $> 40 \times 10^9/L$ unless from rescue transfusions. Subjects failed at least one line of therapy outlined above with a clinical diagnosis of immune mediated thrombocytopenia.

- Anemia, transfusion dependent, or defined as hemoglobin ≤ 9 g/dL for 3 consecutive available readings at least 2 weeks apart, after other cell lines have engrafted OR if hemoglobin 9-10 g/dL, subject must have symptomatic anemia or ongoing treatment for immune hemolytic anemia that have failed at least one line of therapy outlined above. Symptomatic anemia is defined as anemia with fatigue, weakness, shortness of breath, palpitations/fast heartbeat, lightheadedness, and/or chest pain, and these symptoms are attributed to anemia. Laboratory evaluation are recommended but not required for the diagnosis, such as a positive DAT, low haptoglobin $<$ lower limit of normal (LLN), indirect bilirubin $>$ upper limit of normal (ULN), or lactate dehydrogenase (LDH) $>$ ULN.
- Subjects must test negative for HIV, HBV, and HCV by standard serologic tests within the previous six months

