6.6 TRANSFUSIONS

During the study period, packed RBC transfusion should be administered when hemoglobin <7g/dL, or <9g/dL with symptoms; platelet transfusion should be administered when platelet count <10g/dL. Additional transfusions may be administer per the discretion of the PI or the local HCT provider. The number of units transfused should be documented.

Transfusions between scheduled study visits can be done locally or at the sites per institutional standards.

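### The transfusion and growth-factor endpoint uses a one-week baseline, half the period over which the protocol defines transfusion dependence, so the comparator is noisy

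*Combined protocol and SAP*

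**What the plan says.** The synopsis (1.1) and Section 4 give secondary endpoint 2 in the same terms. The quantity is "Average weekly requirement of transfused blood component or growth factor requirement", in units of red cells or platelets per week and total growth-factor dose per week. It is assessed by week 12, "compared to the week prior to the start of the study drug".

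Section 5.1 lists transfusion dependence as one of three alternative routes to eligibility: "Or remains transfusion dependent (≥ 1 transfusion(s)/2 weeks". The other two are failure of, or relapse after, prior therapy and steroid dependence ("Or is steroid dependent").

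On data capture, Section 6.6 covers transfusions given during the study: "The number of units transfused should be documented". The schedule of activities (1.3) has transfusion support evaluated from week -1. Neither gives a longer look-back. Sections 9.3.1 and 9.3.3 plan descriptive summaries, with paired or regression analysis optional, and say nothing about a baseline of zero.

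A longer window does exist for the blood counts. The hemoglobin and platelet baseline in Section 4 is the mean of two values taken "within 14 days of the start of the study drug". That definition does not extend to transfusions or growth factor.

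**The concern.** The baseline window is half as long as the period the protocol itself uses to recognise transfusion need. A subject transfused once a fortnight meets the entry definition, yet may have no transfusion in the week that serves as comparator. That subject can only stay level or appear to worsen. A subject whose transfusion happens to fall in that week starts at twice the true weekly rate and appears to improve.

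The trial has no control arm, so the pre-treatment value is the only comparator. Less transfusion and growth-factor support is part of the study hypothesis (Sections 2.2 and 2.3.3), and this is the endpoint that measures it. A noisy baseline limits what the endpoint can show with about 20 subjects.

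**Working it through.** The plan states no figure for this endpoint, so there is none to reproduce.

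**Inputs from the documents.** Baseline window: 1 week (Section 4). Minimum rate for dependence: 1 transfusion per 2 weeks, or 0.5 per week (Section 5.1). Planned number: 20 (Section 3.1).

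**Assumptions.** The documents give no distribution of transfusion timing, so three spacing models are used. The on-treatment value is taken as the average over all 12 weeks. The counts are transfusion episodes, whereas the endpoint counts units and growth-factor dose.

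**Step 1: chance of no transfusion in the baseline week, at 0.5 per week.**

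- Regular 14-day spacing with random start: 1 − 0.5 × 1 = 50%.
- Poisson: exp(−0.5) = 0.607, or 61%.
- Poisson, given at least one transfusion in the last 2 weeks: exp(−0.5) × (1 − exp(−0.5)) / (1 − exp(−1)) = 0.378, or 38%.

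At 1 transfusion per week the share is 0% with regular spacing and exp(−1) = 37% with Poisson counts.

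**Step 2: effect on individual subjects with no true change, at 0.5 per week** (simulation of 400,000 subjects).

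- Regular spacing: half have a baseline of 0 against 0.5 on treatment and look worse. Half have a baseline of 1 against 0.5 and look 50% better.
- Poisson: 61% look worse and 27% look at least 50% better.
- The mean change is 0.00 under both models. The errors cancel in the group mean.

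**Step 3: variance of the change (12-week average minus baseline over W weeks).** With Poisson counts and no true change this is rate × (1/W + 1/12). The proportional fall does not depend on the rate. The last two columns are at 0.5 per week.

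| Baseline | Variance ÷ rate | Fall against 1 week | Zero baseline, regular | Zero baseline, Poisson |
|---|---|---|---|---|
| 1 week | 1 + 1/12 = 1.083 | – | 50% | 61% |
| 2 weeks | 1/2 + 1/12 = 0.583 | 1 − 0.583/1.083 = 46% | 0% | 37% |
| 4 weeks | 1/4 + 1/12 = 0.333 | 1 − 0.333/1.083 = 69% | 0% | 14% |

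**Step 4: illustration for the group estimate.** Suppose all 20 subjects are at 0.5 per week and need truly halves, a fall of 0.25 per week. The variance per subject is 0.5/W + 0.25/12, and the 95% half-width is 1.96 × √(variance/20):

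- 1 week: variance 0.521, half-width 0.32.
- 2 weeks: variance 0.271, half-width 0.23.
- 4 weeks: variance 0.146, half-width 0.17.

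With the one-week baseline the half-width exceeds the assumed effect. With two weeks it is just below it, and with four weeks clearly below.

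**The case against.** The case for leaving the endpoint alone is that it is one of six secondary endpoints and is summarised descriptively. The only hypothesis test (Sections 9.1 and 9.3.2) concerns the primary endpoint, which already requires no transfusion in the preceding 7 days. The sizes above apply near the minimum of the definition. Dependence means at least one transfusion per two weeks, and heavier users are less affected. Subjects who enter by another route may truly need no transfusion, and for them a longer window changes nothing. The mix of subjects is not given, so the number affected among 20 is unknown. All of this stands and limits the weight of the point. It does not remove the mismatch between the two windows.

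A reader might infer that the one-week baseline biases the result towards benefit through regression to the mean. The documents do not support that. No rule ties the first dose to a heavy week. The requirement in Section 4 that baseline counts be at least 72 hours from a transfusion could instead favour starting in a light period. A link between timing and baseline is possible, but its direction is not established.

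A longer window also has a drawback. Section 5.1 requires stable concomitant therapy for only 15 days before enrollment, so a 28-day baseline can include time on a different regimen. Entry is allowed from day 60 after transplant, so 28 days can reach back to about day 32 (60 − 28). This objection stands and shapes the fix.

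**Conclusion.** The point holds as one of precision. For a subject at the minimum of the dependence definition, the chance of a zero baseline is about half (38% to 61%, depending on the assumed spacing). At 1 transfusion per week it is 0% to 37%. The consequences are a noisy comparator, some dependent subjects who cannot show improvement, and a wide interval for the change. The group mean change is unbiased provided that the start of drug is unrelated to transfusion timing.

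Two further inferences would go too far. It does not follow that half of all enrolled subjects would start at zero for this reason: the documents give no transfusion frequencies, and dependence is only one entry route. Nor do the documents rank this as the leading measure of clinical benefit.

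The variance figures rest on Poisson episode counts and a 12-week average. The interval widths also assume that every subject is at the minimum rate. The primary endpoint, sample size and power are unaffected. This is a cheap improvement to a descriptive endpoint.

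**What to change.** In Section 4, with matching text in the synopsis and Section 9.3.3:

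- Define the baseline for secondary endpoint 2 as average weekly units, and average weekly growth-factor dose, over the 14 days before first dose. This matches the dependence definition and the window already used for the hemoglobin and platelet baseline, and it stays within the 15-day stable-therapy requirement.
- Report a 28-day baseline as a sensitivity analysis where records allow, noting any change of therapy within that window.
- Report absolute rather than percent change, so that subjects with a zero baseline remain usable. This is needed even with the longer windows, because under the Poisson model at the minimum rate 37% (14 days) or 14% (28 days) would still start at zero.

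The cost is wording plus 1 to 3 more weeks of transfusion and growth-factor history per subject. Some of it would come from local providers, since Section 6.6 allows local transfusion between visits. For many subjects the period is already under review: three readings at least two weeks apart, as Section 5.1 requires for thrombocytopenia and for one anemia route, span at least 28 days. Unit totals and growth-factor doses would still have to be abstracted. No extra visit, sample or subject is needed.

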5 STUDY POPULATION

Subject inclusion and exclusion criteria will be reviewed as appropriate by a member of the site's study team. If there is any uncertainty, the PI will make the final decision as to whether a potential subject is eligible for study enrollment.

5.1 INCLUSION CRITERIA

- Ages 18-75 years inclusive
- Ability to comprehend the investigational nature of the study and provide informed consent
- Female patients of reproductive potential agree to avoid pregnancy through abstinence or the use of two forms of highly effective birth control during and for 1 month after the last study treatment and agree not to donate eggs during this time
- Male patients of reproductive potential agree to avoid pregnancy of a partner through abstinence or the use of two forms of highly effective birth control during and for 1 month after the last study treatment and agree not to donate sperm during this time.
- Diagnosis of an immune mediated cytopenia (anemia and/or thrombocytopenia)[‡] in a patient that either:
 - Failed or relapsed after at least one line of therapy including steroids, IVIG, TPO mimetics, rituximab, azathioprine, cyclophosphamide, cyclosporine, tacrolimus, danazol, vincristine, ESA or splenectomy
 - Or remains transfusion dependent (≥ 1 transfusion(s)/2 weeks)
 - Or is steroid dependent*
- Subjects are ≥ 60 days post-allogeneic transplant with:
 - Thrombocytopenia, defined as average platelets count $< 30 \times 10^9/L$ for 3 consecutive available readings at least 2 weeks apart, after other cell lines have engrafted, with no counts $> 40 \times 10^9/L$ unless from rescue transfusions. Subjects failed at least one line of therapy outlined above with a clinical diagnosis of immune mediated thrombocytopenia.

- Anemia, transfusion dependent, or defined as hemoglobin ≤ 9 g/dL for 3 consecutive available readings at least 2 weeks apart, after other cell lines have engrafted OR if hemoglobin 9-10 g/dL, subject must have symptomatic anemia or ongoing treatment for immune hemolytic anemia that have failed at least one line of therapy outlined above. Symptomatic anemia is defined as anemia with fatigue, weakness, shortness of breath, palpitations/fast heartbeat, lightheadedness, and/or chest pain, and these symptoms are attributed to anemia. Laboratory evaluation are recommended but not required for the diagnosis, such as a positive DAT, low haptoglobin $<$ lower limit of normal (LLN), indirect bilirubin $>$ upper limit of normal (ULN), or lactate dehydrogenase (LDH) $>$ ULN.
- Subjects must test negative for HIV, HBV, and HCV by standard serologic tests within the previous six months
- Subjects on other standard of care therapeutic regimens for GVHD or cytopenias should be on a stable dose of medication (no change $\geq 25\%$) for at least 15 days prior to enrollment.
- Patients with a history of hypertension should be maintained on a stable antihypertensive regimen and with controlled blood pressure (Systolic blood pressure < 140 mmHg and diastolic blood pressure < 90 mmHg) for at least one week prior to enrollment.
- Peripheral blood or bone marrow T-cell chimerism $\geq 50\%$ donor cells
- [‡] Immune mediated anemia in subjects with auto or alloantibodies identified due to ABO or non-ABO mismatch transplant, or thrombocytopenia due to identified HLA/HPA antibody. Other causes of immune mediated cytopenias include clinically diagnosed (with or without serologic confirmation) idiopathic thrombocytopenic purpura or autoimmune hemolytic anemia. Subjects with cytopenias attributable to GVHD will be included. Subjects with idiopathic immune mediated cytopenias can also be included. Subjects with evidence for graft rejection per the investigator's opinion ARE NOT eligible for treatment.

* Steroid dependence is defined as inability to tolerate a corticosteroid taper after demonstrating a response to an initial corticosteroid dose (typically 1-2 mg/kg/day). Patients will meet our definition of steroid dependence if their cytopenias relapse or progress before achieving a 50% decrease in the initial corticosteroid dose and/or are unable to have their steroid dose tapered to a dose of less than 20 mg/day of prednisone.

